## 8.2.2 DRS-R-98

During the assessment period, the qualified rater will review the medical record including the nursing record and question from the participant. The necessary information for the assessment will be collected from the family of the participant and/or the site staff as well, as

needed. Based on this information, the rater will assess the condition of the participant since the last assessment using the items specified in DRS-R-98 once daily in morning at least. The scores will be recorded.

At the follow-up visit, the qualified rater will collect the necessary information from the interview of the participant (and his/her family or site staff(s), and/or the medical record, as needed), and assesses items specified in DRS-R-98. The scores will be recorded.

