Surgery (Only for elective surgery)				X (Day 2 or Day 3)				For acute disease, the need for surgery, the timing of surgery and the operative method is not limited.

Study Period:	Screening	g Period	(Fr		sessment Per dose to last a	iod ssessment visit)	Follow-up Period	Notes
Visit Title:	Screening	Baseline		Last Assessment H		Follow-up	Screening Period: For the participant	
Visit Number:	1	2	2	3	4	Discontinuation of study medication	5	hospitalized due to acute disease, the randomization is performed within 24 hours after admission. For the
Visit Timing (Allowance): Efficacy	Acute disease: within 24 hours Elective surgery: within 14 days	Da Before Randomi- zation	y 1 After Randomi- zation	Day 2 to Day 7	The next day after last dose		14 days post last dose (± 3 days)	participant hospitalized due to elective surgery, the procedures of Visit 1 are performed within 14 days before admission . When Visit 1 and Visit 2 are the same day, the overlapping procedures at both visits (e.g., checking the inclusion/exclusion criteria) should be performed only once. If the allowance range is not described, the visit does not have the allowance.
Procedures								
DSM-5		Х	х	X (every day)	X	Х		Assess if the participant develops delirium after randomization and maximum of 3 hours prior to the first dose. If the assessment before randomization is performed within 3 hours before the first dose, the re-assessment after randomization is not needed. At Visit 3 and Visit 4, assess in the morning.
DRS-R-98		Х		X (every day)	X	Х	X	At Visit 3 and Visit 4, assess in the morning.
RCSQ		Х		X (every day)	Х	Х		In the assessment period, assess in the morning.

Study Period:	Screening	g Period	(Fr		sessment Per lose to last a	iod ssessment visit)	Follow-up Period	Notes
Visit Title:	Screening	Baseline	(11)			Assessment	Follow-up	Screening Period: For the participant
Visit Number:	1	2	2	3	4	Discontinuation of study medication	5	hospitalized due to acute disease, the randomization is performed within 24 hours after admission . For the

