## **Medical Conditions**

- 1. Has moderate or severe dementia.
- 2. Has whose APACHE II is 31 or more at Screening (Only for acute disease).
- 3. Has a history of epilepsy or Parkinson's disease.
- 4. Currently uses any of psychotropic agents, or has unstable mental condition including schizophrenia, other mental diseases, bipolar disorder and major depression.
- 5. Has a history of drug or alcohol abuse within 5 years before Screening, or consumes over 60 g per day of alcohol on average (e.g., 60 g alcohol is 3 *goes* of Japanese sake, 3 middle bottles of beer, or 5 glasses of wine), or has alcoholic disease such as alcoholic liver disease or gastritis alcoholic.
- 6. Has delirium as assessed by DSM-5 or DRS-R-98 (total score ≥14.5) during the screening period.
- 7. Is at imminent risk of self-harm or of harm to others in the opinion of the investigator. Participants must be excluded if they report suicidal ideation with intent, with or without a plan or method in the *past 2 months* or suicidal behavior in the *past 6 months*.
- 8. Has history of narcolepsy or cataplexy.
- 9. Has history of hypersensitivity to suvorexant.
- 10. Meets any contraindication or warning listed on package inserts of suvorexant and which are not contained in the exclusion criteria of this protocol.

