#### 8.9.1 Screening Period (from Screening until First Dose of Study Medication)

#### 8.9.1.1 Screening/Visit 1

After the documented informed consent from the participant, the investigator will review whether he/she meet the inclusion and does not meet exclusion criteria.

*Note: For participants hospitalized due to acute disease, APACHE II and ECOG PS will be assessed.* 

Note: For participants hospitalized due to elective surgery, the operative method (i.e., surgery requiring general anesthesia) will be confirmed.

After completing the above, the participants will be registered.

In case Visit 1 and Visit 2 occur on the same day, the overlapping procedures at both visits (e.g., reviewing the inclusion/exclusion criteria) specified in SoA should be performed only once.

In case Visit 1 and Visit 2 occur on different days, the procedures of Visit 1 and the randomization should be performed within 24 hours after admission for participants hospitalized due to acute disease, and the procedures of Visit 1 should be performed within 14 days before admission for participants hospitalized due to elective surgery.

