## 8.9.1.2 Baseline/Visit 2 (until Randomization)

The qualified rater will assess DSM-5 and DRS-R-98 on the day of randomization. The participant will complete RCSQ.

After reviewing whether the participant meets the inclusion and does not meet exclusion criteria based on the above assessments, the eligible participant will be registered and randomized. In addition, the participant will receive appropriate non-pharmacotherapy based on his/her condition (See Section 5.3.1).

The received randomization number will be entered in the participant identification card. The study medication will be prescribed to the participant according to the Component ID. The investigator will instruct the participant to take one tablet of study medication once daily orally before bedtime from the day.

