# 8.9.1.3 Visit 2 (from Randomization until First Dose of Study Medication)

Within 3 hours before the first dose of study medication, the qualified rater will assess DSM-5 again to confirm whether the participant does not develop delirium after randomization. If the assessment before randomization is performed within 3 hours before the first dose of study medication, the re-assessment after randomization is not needed.

If the participant has symptom suspected delirium after the rater assessed before the first dose of study medication, the rater will reassess DSM-5 based on the information to confirm whether the participant does not develop delirium. If the rater judges the participant develops delirium as assessed by DRM-5 or if the rater cannot deny that the participant develops delirium as assessed by DRM-5, the participant must be discontinued from the study without administering study medication.

After the rater assessed before the first dose of study medication, in the case that the participant did not have symptom suspected delirium or in the case that the rater assessed the participant had not developed delirium even if he/she had symptom suspected delirium, the study medication will be administered to him/her.

The investigator or the clinical research coordinator will enter whether the participant had initiated to take the study medication or not to IRT.

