#### 9.4.1 Efficacy Endpoints

The primary efficacy endpoint is the proportion of participants with delirium during the assessment period as assessed by DSM-5.

The secondary efficacy endpoints are:

1. Severity of delirium during the assessment period as assessed by DRS-R-98, defined as the maximum (i.e., worst) of total score among those obtained daily during the assessment period.

2. Proportion of participants with delirium during the assessment period assessed by DRS-R-98, defined as the proportion of participants with the maximum total score of 14.5 or greater during the assessment period.

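### The Day 2 DRS-R-98 rating looks back past the first dose, so some pre-drug symptoms can enter both DRS-R-98 secondary endpoints (minor)

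*Combined protocol and SAP*

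**What the plan says.** **Recall window.** Section 8.2.2 has the rater work backwards: "the rater will assess the condition of the participant since the last assessment using the items specified in DRS-R-98". Section 4.2.1.1 gives the same principle for DSM-5 and DRS-R-98 alike.

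**Baseline.** Section 8.9.1.2 places the last pre-dose DRS-R-98 before randomization: "The qualified rater will assess DSM-5 and DRS-R-98 on the day of randomization". The first dose follows at bedtime the same day (Section 8.1.12).

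**Between randomization and dose.** Section 8.9.1.3 repeats one instrument only: "Within 3 hours before the first dose of study medication, the qualified rater will assess DSM-5 again". The Schedule of Activities (Section 1.3) agrees. The DSM-5 row has a mark in the column after randomization on Day 1 and the DRS-R-98 row has none. The note for later DRS-R-98 ratings is "At Visit 3 and Visit 4, assess in the morning".

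**Endpoints.** Section 1.2 starts the assessment period at the first dose. Section 9.4.1 defines severity as the "maximum (i.e., worst) of total score among those obtained daily" in that period, and DRS-R-98 delirium as that maximum reaching 14.5.

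**The concern.** Both secondary endpoints are meant to describe what happens from the first dose onward. If the first on-treatment rating also scores the hours before the dose, the endpoints contain symptoms that the drug could not have influenced. Under randomization and blinding these should be similar in the two arms, so the expected result is some dilution of the treatment difference.

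The DSM-5 and DRS-R-98 delirium rates would also cover slightly different at-risk periods. That makes the DRS-R-98 result a less clean companion to the primary result.

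**Working it through.** The documents give no figure on this point, so the check sets the timing rules side by side.

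1. **Length of the pre-dose part.** Let h be the time from the baseline DRS-R-98 rating to the first dose. The Day 2 window is h plus the time from dose to the Day 2 rating. No section fixes h. Section 8.9.1.3 waives the second DSM-5 assessment when the pre-randomization one falls within 3 hours of the dose. If DRS-R-98 is rated at that same sitting, h is at most 3 hours. If randomization is earlier in the day, h is longer.

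2. **Same question for DSM-5.** DSM-5 also looks back to its last assessment (Section 8.2.1), but that assessment is never more than 3 hours before the dose, and suspected symptoms after it require reassessment before dosing (Section 8.9.1.3). The primary endpoint is therefore largely protected.

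3. **How the score enters the analysis.** Section 9.4.1 selects scores by when they were obtained. The Day 2 score is obtained after the first dose, so it enters whole. No rule in Section 9 removes its pre-dose part.

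4. **Who can be affected.** A participant with DSM-5 delirium before dosing, or in whom the rater cannot rule it out, is not dosed (Section 8.9.1.3) and so is outside the Full Analysis Set (Section 9.5.1). Both secondary endpoints use that set (Table 5), so this protects the maximum score as well as the binary endpoint. What remains is a raised DRS-R-98 in someone in whom delirium has been ruled out. Section 4.2.1.1 accepts that scores alone may not settle the diagnosis, so such cases can exist. Section 8.2.1 has DSM-5 raters refer to DRS-R-98 information in principle, which narrows the group.

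5. **When an endpoint changes.** Write S for the recorded Day 2 total, S* for the total from post-dose symptoms only, and M for the highest total on later days.
   - Severity: recorded max(S, M), intended max(S*, M). They differ only if S > S* and S > M, so Day 2 must be the worst day.
   - Binary: they differ only if S ≥ 14.5 while S* and M are both below 14.5.

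6. **Is Day 2 likely to be the worst day?** Section 4.3.2 puts frequent onset at about 3 days after admission (acute disease) or after surgery. Counting the admission or surgery day as day 0:
   - Acute, dosed on the admission day: study Day 1 + 3 = Day 4. Dosed the next day: Day 3.
   - Elective, surgery on Day 2 or Day 3 (Section 1.3): Day 5 or Day 6.

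   All fall after Day 2. If the admission or surgery day is counted as day 1, each moves one day earlier, and only the acute group dosed the day after admission reaches Day 2. In the elective stratum the pre-dose hours also precede the surgery. This makes Day 2 an unlikely worst day for delirium. It says nothing about which day is worst in participants who never become delirious.

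**The case against.** The strongest reply is that the text, read as a whole, already implies the restriction. Section 8.2.2 describes rating within the assessment period, and Section 4.2.1.1 gives the purpose of the look-back as catching symptoms that arise in that period. Nowhere does the protocol say that pre-dose symptoms should count, and the rater manuals are separate documents (Section 8.2) that may already start the Day 2 window at the first dose. This stands in part: the flaw is a conflict between the recall instruction and the period definition, not a decision to score pre-drug symptoms. But the only recall instruction in the protocol runs back to the last assessment, and neither Section 8 nor Section 9 makes an exception for Day 2.

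It can also be said that the pre-dose DSM-5 check is strict, that delirium tends to come later than Day 2, and that the secondary objectives carry no stated hypothesis and no power claim. All of this stands and is why the point is minor.

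Finally, the continuous look-back was chosen so that nothing is missed, and cutting it at the dose leaves some pre-dose hours without a DRS-R-98 score. That is true, but those hours lie outside the period that the endpoints describe.

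**Conclusion.** The point holds as a minor inconsistency. As written, the Day 2 DRS-R-98 rating includes pre-dose hours, and symptoms short of a possible DSM-5 diagnosis can enter both secondary endpoints. The effect is probably small and, assuming blinding holds, similar in both arms. This rests on the protocol and SAP text alone; a rater manual that starts the Day 2 window at the first dose would remove the problem in practice.

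Three stronger readings are tempting, and the documents support none of them.

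- **An eligibility breach.** Exclusion 6 reads "Has delirium as assessed by DSM-5 or DRS-R-98 (total score ≥14.5) during the screening period", and the title of Section 8.9.1 is "Screening Period (from Screening until First Dose of Study Medication)", so a reader might infer that participants who reach 14.5 after randomization are dosed against the criteria. But eligibility is reviewed before randomization (Sections 1.3 and 8.9.1.2). After that a separate rule applies, consistently based on DSM-5 (Sections 7.1 and 8.9.1.3). The look-back point does not need Exclusion 6.
- **A stated loss of power.** A reader might apply the 30% and 11.6% of Section 9.9.1 and assume a share of participants positive from pre-dose symptoms. Those rates are for the primary DSM-5 endpoint. The documents give no DRS-R-98 rate, no pre-dose share and no fixed interval, so any such figure would be assumption throughout.
- **Bias in favor of the drug.** Pre-dose symptoms cannot depend on treatment, so dilution is the expected direction, not a false positive.

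**What to change.** In Sections 8.2.2 and 8.9.2, state that the Day 2 DRS-R-98 rating scores only symptoms from the first dose onward. Mirror this in Section 9.4.1 by defining the maximum over daily totals that rate symptoms after the first dose, and check that the rater manual says the same.

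Optionally, add a sensitivity analysis of both secondary endpoints without the Day 2 rating. It would also discard genuine first-night symptoms, and it needs a stated rule for participants whose only post-dose rating is on Day 2, so it should support the main analysis and not replace it.

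The cost is about one sentence in each place. No extra rating or visit is needed. The downside is that raters must separate pre-dose from post-dose notes for one rating, which depends on the notes being timed.

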## 8.2.3 Richards Campbell Sleep Questionnaire (RCSQ) Score

During the assessment period, the participant will complete 5-item visual analog scale (VAS) about the last-night sleep in the sleep questionnaires once daily in the morning. The clinical coordinator measures the mark written by the participant with a ruler and enters it in millimeter (mm) unit in the eCRF.

# 8.2.4 Undesirable Hospitalized Patient Outcomes (Fall, Accidental or Intentional Catheter/Tube Removal, and Body Restraint)

The investigator will collect the information related to all events of falls, accidental or intentional catheter/tube removal (i.e., transfusional line, bladder catheter, drain), and body restraints which occur during hospitalization (including the follow-up period when the participant is hospitalized). When falls, accidental or intentional catheter/tube removal, and/or body restraints occur, the investigator will evaluate its relationship to delirium referring to the following criteria.

- Related to delirium: There is evidence of occurrence of delirium. The temporal sequence of the undesirable hospitalized patient outcome onset relative to the occurrence of delirium is reasonable. The undesirable hospitalized patient outcome is more likely explained by delirium than by another cause, e.g., an adverse event other than delirium, a patients' background and/or an environmental factor including use of a concomitant medication or a complication.
- Not related to delirium: Participant did not develop delirium OR temporal sequence of the undesirable hospitalized patient outcome onset relative to the occurrence of delirium is not reasonable OR the undesirable hospitalized patient outcome is more likely explained by another cause than delirium.

"Fall" should be entered in AE eCRF as ECIs as well.

#### 8.3 Safety Assessments

Details regarding specific safety procedures/assessments to be performed in this study are provided.

Planned time points for all safety assessments are provided in the SoA.

#### 8.3.1 Physical Examinations

A physical examination will be conducted by the investigator at Screening as per institutional standard evaluations, the last assessment visit and the follow-up visit.

#### 8.3.2 Vital Signs

Blood pressures, pulse rate, and body temperature will be measured once daily from the day of Randomization to the last assessment visit. It is preferred that vital signs are utilized same procedure, same position/side and the same timing of procedure throughout the study.

Blood pressure and pulse rate measurements should be preceded by at least 5 minutes of rest for the participant in a quiet setting without distractions.

For the participants hospitalized due to acute disease, the measurements of heart rate and respiratory rate are necessary at Screening for assessment of APACHE II.

#### 8.3.3 Clinical Safety Laboratory Assessments

Refer to Appendix 2 for the list of clinical laboratory tests to be performed and to the SoA for the timing and frequency.

- The investigator or medically qualified designee (consistent with local requirements) must review the laboratory report, document this review, and record any clinically relevant changes occurring during the study in the AE section of the CRF. The laboratory reports must be filed with the source documents. Clinically significant abnormal laboratory findings are those which are not associated with the underlying disease, unless judged by the investigator to be more severe than expected for the participant's condition.
- All protocol-required laboratory assessments, as defined in Appendix 2, must be conducted in accordance with the laboratory manual and the SoA.
- If laboratory values from nonprotocol-specified laboratory assessments performed at the institution's local laboratory require a change in study participant management or are considered clinically significant by the investigator (eg, SAE or AE or dose modification), then the results must be recorded in the appropriate CRF (eg, SLAB).
- For any laboratory tests with values considered clinically significantly abnormal during participation in the study or within 14 days after the last dose of study intervention, every attempt should be made to perform repeat assessments until the values return to normal or baseline or if a new baseline is established as determined by the investigator.

## 8.3.4 Modified Cataplexy Questionnaire (MCQ) Review

If the investigator receives a report that the participant had cataplexy including cataplexy-like event or fall after randomization, he/she will ask the participant to complete the MCQ (a modified version of Cataplexy Questionnaire [Anic-Labat S, et al. 1999]) and will review it.

If an event is fall, the investigator will review MCQ in order to rule out cataplexy. The administration of the MCQ is provided in a separate document.

All reports of cataplexy including cataplexy-like event and fall, which occurred after randomization, must be recorded as ECIs (See Section 8.4.7). The MCQ, administered in conjunction with documentation of these, will be provided to the CAC.

Falls which occur during hospitalization must be reported as Undesirable Hospitalized Patient Outcomes as well (See Section 8.2.4).

## 8.4 Adverse Events, Serious Adverse Events, and Other Reportable Safety Events

The definitions of an AE or SAE, as well as the method of recording, evaluating, and assessing causality of AE and SAE and the procedures for completing and transmitting AE, SAE, and other reportable safety event reports can be found in Appendix 3.

Adverse events, SAEs, and other reportable safety events will be reported by the participant (or, when appropriate, by a caregiver, surrogate, or the participant's legally authorized representative).

The investigator and any designees are responsible for detecting, documenting, and reporting events that meet the definition of an AE or SAE as well as other reportable safety events. Investigators remain responsible for following up AEs, SAEs, and other reportable safety events for outcome according to Section 8.4.3.

The investigator, who is a qualified physician, will assess events that meet the definition of an AE or SAE as well as other reportable safety events with respect to seriousness, intensity/toxicity and causality.

# 8.4.1 Time Period and Frequency for Collecting AE, SAE, and Other Reportable Safety Event Information

All AEs, SAEs, and other reportable safety events that occur after the participant provides documented informed consent, but before intervention randomization, must be reported by the investigator if the participant is receiving placebo run-in or other run-in treatment, if the event causes the participant to be excluded from the study, or is the result of a protocol-specified intervention, including but not limited to washout or discontinuation of usual therapy, diet, or a procedure.

From the time of intervention randomization through 14 days after cessation of study intervention, all AEs, SAEs, and other reportable safety events must be reported by the investigator.

Additionally, any SAE brought to the attention of an investigator at any time outside of the time period specified in the previous paragraph must be reported immediately to the Sponsor if the event is considered related to study intervention.

Investigators are not obligated to actively seek AEs or SAEs or other reportable safety events in former study participants. However, if the investigator learns of any SAE, including a death, at any time after a participant has been discharged from the study, and he/she considers the event to be reasonably related to the study intervention or study participation, the investigator must promptly notify the Sponsor.

All initial and follow-up AEs, SAEs, and other reportable safety events will be recorded and reported to the Sponsor or designee within the time frames as indicated in Table 4.

Type of Event	Reporting Time Period: Consent to Randomization/ Allocation	Reporting Time Period: Randomization/ Allocation through Protocol-specified Follow-up Period	Reporting Time Period: After the Protocol- specified Follow-up Period	Time Frame to Report Event and Follow-up Information to Sponsor:
NSAE	Report if: - due to protocol- specified intervention - causes exclusion - participant is receiving placebo run-in or other run-in treatment	Report all	Not required	Per data entry guidelines
SAE	Report if: - due to protocol- specified intervention - causes exclusion - participant is receiving placebo run-in or other run-in treatment	Report all	Report if: - drug/vaccine related. (Follow ongoing to outcome)	Within 24 hours of learning of event
ECI (require regulatory reporting)	Report if: - due to intervention - causes exclusion	Report - Potential DILI - Require regulatory reporting	Not required	Within 24 hours of learning of event
ECI (do not require regulatory reporting)	Report if: - due to intervention - causes exclusion	Report - non-DILI ECIs and those not requiring regulatory reporting	Not required	Within 5 calendar days of learning of event
Cancer	Report if: - due to intervention - causes exclusion	Report all	Not required	Within 5 calendar days of learning of event
Overdose	Report if: - receiving placebo run- in or other run-in medication	Report all	Not required	Within 5 calendar days of learning of event

Table 4Reporting Time Periods and Time Frames for Adverse Events and OtherReportable Safety Events

DILI=drug-induced liver injury; ECI=event of clinical interest; NSAE=nonserious adverse event; SAE=serious adverse event

